#### 8.1.2 Appetite Suppression

The null and alternative hypotheses are:

$$H_0$$
:  $π_T ≤ π_C$ 
 $H_1$ :  $π_T > π_C$ 

Where  $\pi_T$  and  $\pi_C$  are the probabilities of appetite suppression in treatment versus control respectively. Pearson correlation will be utilized to correlate appetite score (as measured with TFEQ-18V2; ) with stimulation dose. Estimates of 95% confidence intervals will also be computed for the difference between varying levels of stimulation. Wilcoxon signed rank tests and/or Kruskal Wallis statistics will be utilized to make comparisons between groups as required. Estimates and 95% confidence intervals will also be computed for the difference in appetite levels between Baseline and Therapy Periods.

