#### 5. STUDY DESIGN

Randomized, adaptive parallel arm study. Subjects will be initially screened during a screening period (1 week, ±7 days; Figure 2). During this screening period, prior to study procedures being performed, subjects will sign an informed consent form. Then they will have their

[figure not shown]

Figure 2: Study Outline

weight and blood pressure measured, FOCBP will have a pregnancy test, get blood drawn for analysis (blood lipids, CMP, hemoglobin A1c), and complete patient preference questionnaires. At the end of the screening/baseline period, eligible subjects will be offered the chance to enroll in the study. After enrolling, subjects will be randomized to treatment or control groups.

The Treatment group will be instructed to follow a healthy 1200 calorie diet that they will follow for the duration of the study and will receive training on the use of the weekly paper diary, electronic scale, smartphone app and the Elira wearable patch system. All treatment subjects will be required to stimulate in the office for a period of time to confirm sufficient system training and tolerability of the stimulation. Following this, subjects will enter the Therapy Period, for a 12-week duration.

The Control group will be instructed to follow a healthy 1200 calorie diet that they will follow for the duration of the study and will receive training on the use of the weekly paper diary and electronic scale. The Control group will not receive the electronic smartphone app or the Elira wearable patch system.

At the end of the Therapy Period, subjects will be assessed for weight loss, blood pressure, CMP, blood lipids, HbA1c, and will be terminated from the study.

The study utilizes an adaptive approach where cohorts of enrolled subjects (in groups of 25 per arm) are assessed for dose response and progression to achievement of primary and secondary endpoints. Frequent interim endpoint assessment utilizing Markov-chain Monte Carlo (MCMC) methods coupled with longitudinal analyses will be utilized to determine sample sizes for future cohorts (assessed primarily via Normal dynamic linear modeling [NDLM]).

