#### 6.1.3 Secondary Effectiveness Endpoints:

- Number of subjects reporting >5% total body weight loss at the end of Therapy as compared to Baseline between Treatment and Control
- Percent change in appetite scores at the end of Therapy Period compared to Baseline between Treatment and Control.
- Blood pressure, blood lipids, ALT and HbA1c at the end of Therapy Period as compared to Baseline between Treatment and Control groups.
- % changes in BMI at the end of Therapy Period compared to Baseline between Treatment and Control groups

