### 8. STATISTICAL CONSIDERATIONS AND ANALYSIS PLAN

Categorical variables will be summarized by number and percent. Continuous variables will be summarized by total number (N), mean, standard deviation (SD), median, minimum and maximum. Ninety-five percent, 2-sided confidence intervals on estimated means and differences in means between treatment and control groups will be calculated. Confidence intervals will be similarly computed for proportions and differences between proportions. In addition, propensity score and sensitivity analyses will be utilized to compare adverse events and/or adverse device effects incidence versus historical control. Wilcoxon signed rank tests, Fisher exact tests, and Pearson Correlations will be utilized to compare changes in baseline variables between varying

time points of the study (e.g. baseline versus post stimulation treatment) and to correlate stimulation parameters with endpoint values. Markov-chain Monte Carlo Analyses will be utilized to conduct Bayesian posterior probability distributions with multiple imputations allowed to assess treatment efficacy within and between cohorts. The need for additional endpoints to achieve primary and secondary significance will be determined utilizing longitudinal modeling. Finally, dose response will be modeled and analyzed within and between cohorts to determine optimal therapy dose for stimulation in open label period within and between cohorts using Normal dynamic linear modeling (NDLM) since monotonicity of the response cannot be assumed.

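### Section 8.1.2 allows a paired test for the between-arm appetite comparison without a rule for choosing the valid alternative, and its hypotheses do not match the appetite endpoint

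*Combined protocol and SAP*

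**What the plan says.** Section 5 describes the trial as a "Randomized, adaptive parallel arm study". Section 5.3 randomises subjects with blocking by site and states that the study is open label. Nothing pairs a treated subject with a control.

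Section 6.1.3 lists the appetite endpoint as "Percent change in appetite scores at the end of Therapy Period compared to Baseline between Treatment and Control". This is a continuous quantity contrasted between arms.

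Section 8.1.2 sets out the analysis:

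- Its null and alternative hypotheses are written on two parameters that "are the probabilities of appetite suppression in treatment versus control respectively". No cut-off or responder rule says when appetite counts as suppressed.
- On the test, it says that "Wilcoxon signed rank tests and/or Kruskal Wallis statistics will be utilized to make comparisons between groups as required".
- It closes with "Estimates and 95% confidence intervals will also be computed for the difference in appetite levels between Baseline and Therapy Periods", with no mention of arm.

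The general text of section 8 bears on the point in two ways. It commits to "Ninety-five percent, 2-sided confidence intervals on estimated means and differences in means between treatment and control groups will be calculated". It also states that "Wilcoxon signed rank tests, Fisher exact tests, and Pearson Correlations will be utilized to compare changes in baseline variables between varying" time points, giving baseline against post-treatment as the example. That is the normal within-subject use of signed rank.

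**The concern.** Signed rank takes one difference per subject, or per matched pair, and asks whether those differences centre on zero. Two independent randomised arms supply no such differences. A reader who takes the test name in section 8.1.2 literally has one natural way to run it: on change from baseline within an arm. The Baseline-versus-Therapy estimate that closes the section points the same way.

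That analysis answers a different question from the endpoint. Both arms are told to follow the same 1200-calorie diet and all subjects know their allocation, so appetite scores may move in both arms for reasons unrelated to stimulation. A significant change within the treatment arm would not show that treatment beats control.

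A second and separate fault is that the hypotheses concern the probability of an undefined event while the endpoint is a change in score. The stated null therefore cannot be tested as written, and no listed calculation links it to the endpoint.

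**Working it through.** **Setting the passages side by side**

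| Element | Place | Nature |
|---|---|---|
| Endpoint | 6.1.3 | Continuous, between arms |
| Hypotheses | 8.1.2 | Probability of an undefined event, between arms |
| Signed rank | 8.1.2 | Assigned between groups, but a paired or one-sample test |
| Kruskal-Wallis | 8.1.2 | Assigned between groups, valid for independent arms |
| Signed rank | 8 | Assigned between time points, its proper use |
| Closing estimate | 8.1.2 | Between periods, no arm contrast |
| 95% confidence intervals | 8 | Include between-arm differences in means |

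One of the two tests named for the arm comparison is unsuitable. The words and/or, together with as required, leave the choice open, possibly until after the data are seen. The score is also unsettled: section 8.1.2 names the TFEQ for the dose correlation, while sections 2.1, 5.2 and 9.8 also collect weekly VAS ratings.

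**Size of the possible misreading**

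The documents give no effect size, SD, power or sample size for appetite, so there is no stated figure to reproduce. The inputs are:

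- 75 subjects per arm and 30% dropout (section 8.2, where they serve the weight-loss endpoint). Completers: 75 × (1 − 0.30) = 52.5, taken as 52.
- Assumed: normal change scores with SD 1, the same shift d in both arms (no device effect), d from 0 to 0.5 SD, and two-sided 5% tests.

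Each setting was simulated 4,000 times. The entries are the percentage of trials with p < 0.05.

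| Common shift d (SD) | Signed rank within treatment, n = 52 | Kruskal-Wallis between arms, n = 52 | Signed rank within treatment, n = 75 | Kruskal-Wallis between arms, n = 75 |
|---|---|---|---|---|
| 0 | 4.9 | 5.0 | 4.6 | 5.2 |
| 0.2 | 28 | 5.1 | 38 | 5.3 |
| 0.3 | 54 | 4.6 | 72 | 5.1 |
| 0.4 | 79 | 4.4 | 92 | 5.1 |
| 0.5 | 94 | 5.0 | 99 | 5.0 |

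The two-arm rank-sum test agreed with Kruskal-Wallis to within 0.1 percentage point throughout.

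A normal approximation confirms the signed-rank column: power ≈ Φ(d√(0.955n) − 1.96), where 0.955 = 3/π is the efficiency of signed rank relative to the t test under normality. With n = 52, √(0.955 × 52) = 7.05.

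- d = 0.2: Φ(1.41 − 1.96) = Φ(−0.55) = 0.29
- d = 0.5: Φ(3.52 − 1.96) = Φ(1.56) = 0.94

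**Signed rank on arbitrary cross-arm pairs**

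If someone instead paired treated and control subjects arbitrarily and ran signed rank on the pairs, the rejection rate stayed between 4.5% and 5.6%. That use does not inflate error here, but the plan defines no pairs and the p-value would depend on how they were formed.

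**The case against.** The strongest reply is that the plan already contains what is needed. The criticised sentence names Kruskal-Wallis, which for two arms is equivalent to the rank-sum test. Section 8 promises confidence intervals on between-arm differences in means. The endpoint and the hypotheses both contrast Treatment with Control. A within-arm p-value could stand in for the arm comparison only if all of this were set aside. This stands, and it limits the point to an ambiguity. It does not remove the point, because the general interval statement neither says which test governs appetite nor repairs the hypotheses.

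The simulation can also be challenged. It shows only that a one-sample test detects a one-sample shift. The documents do not say how far, or in which direction, the diet alone would move appetite scores; if scores worsened equally in both arms, the result would not look like a benefit. Completers are not the main set either: secondary effectiveness analyses are modified intent-to-treat (section 8.4) with last value carried forward (section 8.3). The n = 75 columns lie nearer to that set and show the same pattern, but the rates remain conditional on the assumed shift.

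Three stronger readings are tempting, and the documents do not support them:

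- **That the plan offers only a within-arm appetite analysis.** Kruskal-Wallis and the between-arm intervals contradict this.
- **That the probability hypotheses also let a diet effect pass for a device effect.** They compare randomised arms given the same diet. Their fault is an undefined event and a mismatch with the endpoint.
- **That the other continuous secondary endpoints share the fault.** Section 8 uses signed rank "to compare changes in baseline variables between varying" time points, which is proper. The between-group sentence belongs to the appetite section alone.

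**Conclusion.** The point holds as two separate wording defects on a secondary endpoint, and both should be corrected before analysis. First, section 8.1.2 lists a paired test for an unpaired comparison beside a valid test, with no rule for choosing. Second, its hypotheses rest on an undefined event and do not correspond to the listed endpoint. Both follow from the text and need no assumption.

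The consequence is conditional. It arises only if the within-arm signed-rank result is read as the appetite finding and scores improve in both arms. The 28% to 94% range describes that misreading at 52 per arm for common shifts of 0.2 to 0.5 SD. It is not the false-positive rate of the trial's appetite analysis: a proper between-arm rank test holds about 5% at every shift examined.

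**What to change.** Revise section 8.1.2 as follows:

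1. Name the lead appetite score (TFEQ-R18V2 or VAS, and which scale or item of it).
2. Restate the null as no difference between arms in the change in that score, consistent with section 6.1.3. If a responder analysis of suppression is also wanted, define the event.
3. In the between-group sentence, replace signed rank with one pre-specified analysis in the modified intent-to-treat set: ANCOVA of the end-of-therapy score on arm, baseline score and site. Use rank-sum on percentage change as the non-parametric check; for two arms this is equivalent to the Kruskal-Wallis test already named.
4. State openly that the ANCOVA difference is on the score scale, while the rank-sum check stays on the percentage change in the endpoint.
5. Label signed rank and the Baseline-versus-Therapy estimate as within-arm description only.

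Removing signed rank from that sentence and aligning the hypotheses would by itself cure the stated faults. ANCOVA is preferred because it uses the baseline score and the site factor already present in the randomisation. No blanket change to the other secondary endpoints is called for on this ground.

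The cost is SAP wording and a minor extra analysis. Baseline and end-of-therapy scores are already scheduled in both arms, so visits, data collection and sample size are unaffected.

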#### 8.1.3 Weight Loss

The null and alternative hypotheses are:

$$H_0$$
:  $π_T ≤ π_C$ 
 $H_1$ :  $π_T > π_C$ 

Where  $\pi_T$  and  $\pi_C$  are the probabilities of weight loss (% TBWL, %EBWL) in treatment versus control respectively. Estimates of the proportion of weight loss in pounds, % total body weight loss (%TBWL) Excess Body Weight Loss (%EBWL) or BMI will be compared with a tested Fishers Exact Test. Estimates and 95% confidence intervals will also be computed for the difference in rate of weight loss between varying stimulation levels.

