#### 5.3 ASSIGNMENT & BLINDING

Subjects meeting the Inclusion and Exclusion criteria will be enrolled and randomized into either Treatment or Control groups. The randomization algorithm will be blocked to account for site bias and to ensure counterbalance across sites. As this is an open label study, there will be no consideration for blinding.

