#### 6.1.2 Primary Effectiveness Endpoint:

The primary effectiveness endpoint is the percent reduction in total body weight loss (%TBWL), measured as End Weight – Initial Weight divided by Initial Weight, multiplied by 100, at the end of Therapy period compared to Baseline between Treatment and Control.

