#### 8.2 JUSTIFICATION OF SAMPLE SIZE

The calculated sample size for the study is based on conservative imputation of results from other studies on weight loss including the use of TENS for weight loss. The degree of coaching/dietary support throughout the present study is moderate intensity lifestyle/weight coaching. The sample size modeling assumes an average of 3.5% TBWL in Control subjects using diet and exercise alone. The estimated weight loss in the Treatment subjects is modeled from preliminary data on T6/T7 dermatomal TENS when used for weight loss: 7.5% TBWL. The variance of the responses in the study (i.e. Standard Deviation) was modeled at + 5% TBWL. This value was taken from previous dermatomal TENS weight loss study results. The model assumes a 30% drop out rate across groups and an 80% powered endpoint using an adaptive p spending model wherein interim posterior probability assessments are allowed after enrolling proscribe cohorts of not less than 25 subjects per group for not less than 7 weeks of stimulation. The alpha penalty will be minimized per interim by assessing the relationship between stimulation (i.e. dose) and weight loss using Normalized Linear Dynamic Modeling (NLDM) to determine overall sample size projected (i.e. futility) rather than assessing the primary endpoint hypothesis per se. Monotonicity will not be assumed in this analysis. This modeling provides an estimate of 75 subjects per group, for a total study size of 150 subjects. However, the protocol allows for enrollment of additional subjects should the interim model project under powering of the primary endpoint.

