#### 8.3 RETENTION AND HANDLING OF MISSING DATA

Every effort will be made to collect all data at each time point in the study. The PI and the Clinical Data Monitor will minimize the amount of missing data by appropriate management of the prospective clinical trial, proper screening of subjects, and training of clinicians. If a subject misses a dietary entry into either the paper or electronic diary, a look back entry for that value is allowed provide for the week preceding the event. Outside this window, data will be considered missing. All partial data available for subjects who drop out during the course of the study will be included.

For missing data imputation, the last value carried forward method will be utilized. To assess the potential effect of missing data on the primary effectiveness endpoint, the following sensitivity analyses will be performed to impute missing values.

Sensitivity Analyses: First, the primary effectiveness endpoint will be assessed with all missing data points imputed as failures for both groups. Second, the primary efficacy endpoint will be assessed with all missing data points imputed as successes for both groups.

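### Section 8.1.3 tests a probability of weight loss with Fisher's exact test and no cut-off, although the primary endpoint and sample-size inputs are mean %TBWL; no primary test is designated

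*Combined protocol and SAP*

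**What the plan says.** - **Endpoint.** Section 6.1.2 and the Protocol Summary define the primary effectiveness endpoint as %TBWL, "measured as End Weight – Initial Weight divided by Initial Weight, multiplied by 100", compared between arms at the end of therapy. This is a continuous variable.
- **Sample size.** Section 8.2 uses mean %TBWL of 3.5 in Control and 7.5 in Treatment. It adds: "The variance of the responses in the study (i.e. Standard Deviation) was modeled at + 5% TBWL". With 30% dropout and 80% power it arrives at 75 per group. No alpha is given.
- **Hypothesis and test.** Section 8.1.3 sets H0: π_T ≤ π_C against H1: π_T > π_C, where the two parameters "are the probabilities of weight loss (% TBWL, %EBWL) in treatment versus control respectively". Pounds lost, %TBWL, %EBWL or BMI "will be compared with a tested Fishers Exact Test". It gives no threshold and does not say which of the four measures decides.
- **Responder endpoint.** Section 6.1.3 lists, as secondary: "Number of subjects reporting >5% total body weight loss at the end of Therapy as compared to Baseline between Treatment and Control".
- **Missing data.** Section 8.3 carries the last value forward. As a sensitivity analysis, "the primary effectiveness endpoint will be assessed with all missing data points imputed as failures for both groups"; a second analysis imputes successes. Neither term is defined.
- **General methods.** The opening of Section 8 says that 95% "2-sided confidence intervals on estimated means and differences in means between treatment and control groups will be calculated". It also lists signed-rank and Fisher tests, Pearson correlation and a Bayesian MCMC assessment of efficacy. None of these is designated as the primary test.

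**The concern.** The endpoint and the planning values concern a mean; the stated hypothesis and test concern a proportion. Fisher's test cannot be applied to %TBWL until someone decides what counts as weight loss. The >5% threshold does not settle this, because it belongs to a different, secondary endpoint. The success/failure imputation in Section 8.3 depends on the same undefined split, so this is not a slip confined to one sentence.

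The trial is open label (Section 5.3), with frequent interim assessments and possible expansion to 300 subjects (Protocol Summary). The cut-off, the deciding measure and the sidedness could therefore be settled after outcome data have been seen. The Fisher result and the interval for the difference in means can also disagree, and nothing says which one determines success.

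**Working it through.** **1. The plan's own figure.** Inputs from Section 8.2: difference 7.5 − 3.5 = 4, SD 5, power 80%, dropout 30%. Alpha is not stated; two-sided 0.05 is assumed from the 95% two-sided intervals in Section 8.

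n per arm = 2 × (1.960 + 0.842)² × 5² / 4² = 24.5, so 25 evaluable; 25 / 0.70 = 35.7, so 36 enrolled.

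Varying alpha (0.05, 0.025, 0.01), sidedness, power (80%, 90%) and the dropout formula (÷ 0.7 or × 1.3) gives 26 to 68 enrolled per arm. None gives 75. The alpha-spending scheme in Section 8.2 is unspecified, and it would have to about double the sample size (75 / 36 = 2.1), so this cannot be checked. A proportion-based calculation with an assumed cut-off of 0, one-sided 0.05 and no continuity correction gives 52 / 0.7 = 74.3, so 75; but the documents state no such cut-off. The figure of 75 therefore does not reveal which test was meant.

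**2. Number analysed.** 75 × 0.70 = 52.5, taken as 52 per arm if dropouts contribute nothing; 75 if every subject contributes a value.

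**3. Comparison of means.** Noncentral t, two-sided 0.05, noncentrality (4/5) × √(n/2).
- n = 52: 0.8 × 5.10 = 4.08, power 98.1%.
- n = 75: 0.8 × 6.12 = 4.90, power 99.8%.

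**4. Fisher's test at assumed cut-offs.** With normal responses, the probability of exceeding cut-off c is 1 − Φ((c − mean)/5). Power is the sum of the joint binomial probabilities over all tables with a Fisher p-value of at most alpha.

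| Cut-off | Treatment vs Control | Two-sided 0.05, n = 52 / 75 | One-sided 0.05, n = 52 / 75 |
|---|---|---|---|
| >0 | 93.3% vs 75.8% | 62.0% / 81.6% | 74.5% / 89.0% |
| >5% | 69.1% vs 38.2% | 87.6% / 96.6% | 91.3% / 97.9% |
| >10% | 30.9% vs 9.7% | 71.8% / 87.8% | 81.1% / 93.3% |

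At one-sided 0.025 the powers equal the two-sided column, so the one-sided gain comes from the larger alpha.

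**5. Section 8.3 sensitivity analyses.** Assume 75 per arm, 30% missing at random in each arm, and two-sided Fisher at 0.05. A responder probability p becomes 0.7p if missing values are failures and 0.7p + 0.3 if they are successes.

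| Cut-off | Missing as failures: rates, power | Missing as successes: rates, power |
|---|---|---|
| >0 | 65.3% vs 53.1%, 29.1% | 95.3% vs 83.1%, 61.4% |
| >5% | 48.4% vs 26.7%, 74.4% | 78.4% vs 56.7%, 76.7% |
| >10% | 21.6% vs 6.8%, 68.9% | 51.6% vs 36.8%, 41.1% |

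**6. Sign.** Under the Section 6.1.2 formula, loss is negative: the planning means become −7.5 and −3.5. Section 8.2 writes them as positive. If the greater-than alternative in Section 8.1.3 were simply carried over to means, it would point the wrong way unless loss is given a positive sign.

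**The case against.** **A comparison of means is already planned.** Section 8 and the Protocol Summary do promise intervals for differences in means. This stands as far as it goes: the fault is lack of designation, not absence. But the interval is one item in a general list, it is two-sided while the Section 8.1.3 alternative is directional, and nothing ties it to the success decision.

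**The natural cut-off is >5%, and power there is adequate.** At >5% Fisher's test has 87.6% or 96.6% power, above the planned 80%. That is correct, so a power shortfall is not the argument. Adopting >5% would, however, make the primary test duplicate a secondary endpoint and leave the continuous primary endpoint untested.

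**52 per arm is too pessimistic.** Last value carried forward (Section 8.3) and the modified intent-to-treat set (Section 8.4) keep dropouts with a carried-forward weight in the analysis, so the analysed number is nearer 75. There every two-sided Fisher figure in the main comparison exceeds 80%. This is a fair limit on the illustration, though early carried-forward weights could shrink the difference, so 75 with the full effect is optimistic.

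**The sensitivity analyses need not have 80% power.** True; those figures show only how strongly the result depends on an undefined split.

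**Interim looks do not test the primary hypothesis.** Section 8.2 says they model dose against weight loss for futility. The Protocol Summary, however, speaks of assessing interim significance and of enlarging the trial if it is not reached. Section 8.5 requires deviations to be documented and justified in the final report, which does not prespecify the test.

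**Conclusion.** The concern holds and must be fixed. The only stated weight-loss hypothesis and test do not match the primary endpoint, and the test cannot be run without a cut-off that the plan does not give.

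The defect is an undefined primary analysis rather than a demonstrated loss of power. Two-sided, with the same planning values, power runs from 62.0% to 98.1% with 52 per arm and from 81.6% to 99.8% with 75, depending on the test and cut-off chosen. It falls below 80% only with 52 per arm: at >0 and >10% two-sided, and at >0 one-sided.

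These figures assume alpha 0.05, normal %TBWL with a common SD of 5, the planned difference of 4 points, illustrative cut-offs of 0, 5 and 10%, and no interim adjustment. The mismatch itself rests on the text alone and needs none of these assumptions.

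**What to change.** 1. In Section 8.1.3, state the hypothesis on the between-arm difference in mean week-12 %TBWL, with loss given a positive sign.
2. Say which visit supplies the initial weight. Visit 0 is labelled Screening/Baseline, but weight is also taken at Visit 1, and the endpoint definition names neither.
3. Designate one comparison of means as the primary test, with alpha and sidedness, and report the difference with its 95% interval. ANCOVA with baseline weight and site is a suitable option, since Section 5.3 says "The randomization algorithm will be blocked to account for site bias and to ensure counterbalance across sites"; an unadjusted comparison is also valid.
4. Keep Fisher's test, or a site-stratified Cochran–Mantel–Haenszel test, for the >5% responder endpoint.
5. Rewrite the Section 8.3 sensitivity analyses for a continuous outcome, for example by imputing missing week-12 %TBWL over a stated range of values. Confine success/failure imputation to the responder endpoint.
6. Minor: in Section 8.1.2, drop the paired signed-rank test for between-group comparisons; the Kruskal–Wallis test already listed there is valid.

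The cost is wording in the analysis plan. All the variables are already collected.
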